### (c) Human Studies:

***Participants and Recruitment:*** All possible participants recruited for this study will be Veterans. Participants will be referred from three primary sources: 1) Clinical services; 2) TRACTS; (3) Community partners, other VA clinical services, and advertisements.

1) Clinical services: VA Boston Healthcare System (VABHS) clinics often include: Center for Returning Veterans, Polytrauma, Primary Care, Neuropsychology, Psychology, Neurology, Psychiatry, and PTSD Clinics (Behavioral Health and Women's Division). IRB-approved study brochures will be placed in clinics, and staff members working in these clinics will share approved recruitment materials for STEP-Home and refer Veterans who may be appropriate for the trial.

2) TRACTS: Current/former TRACTS participants at TRACTS Boston may be told about STEP-Home by TRACTS study staff. Additionally, a recruitment letter will be sent to former TRACTS participants to explain the study to them and give them STEP-Home study staff contact information should they wish to learn more about participating.

3) Other recruitment sources may include existing community partners (e.g., schools, Veteran Outreach coordinator [name]), VA outpatient clinics/Vet Centers/CBOCS, advertisements, social media (e.g., Facebook), and our website ([www.stephome.hms.harvard.edu](http://www.stephome.hms.harvard.edu)). Any new advertisements will be reviewed by IRB before implementation. Additionally, given the possibility that STEP-Home workshops may be conducted via telehealth methods and advertisements may reach Veterans outside of Massachusetts, we intend to make STEP-Home available to Veterans nationwide.

4) Recruitment at the Houston site will be under the direction of Houston site PI, [name], and will be overseen by their IRB.

5) The Veterans Affairs/Department of Defense Identity Repository (VADIR), a VA database containing military personnel information from the DOD. We will receive quarterly updates from VADIR; the VADIR transfer server ([vaausvdrxfr20.aac.va.gov](http://vaausvdrxfr20.aac.va.gov)) automatically pushes the quarterly file to our study server, via secure transfer behind the VA firewall.

Each month, we will send recruitment letters to a random sample of up to 1000 newly separated Veterans received from VADIR. Specifically, this means that our first month of recruitment will involve sending recruitment letters to up to 1000 randomly selected Veterans who separated from service during the three months prior. The next month, we will exclude Veterans who already received a letter from us and extract another group of up to 1000 Veterans from the larger pool of eligible Veterans who separated from service during the three months prior (which will comprise any Veterans who are still within the window of eligibility and were not selected the previous month as well as any Veterans who are newly separated in the month between recruitment waves). This process will continue until our enrollment target is met. The recruitment letter will briefly describe the study and invite them to contact the study team if they are interested in learning more about participating. They will also have the option of sending back an "opt out" postcard in a pre-paid envelope if they do not wish to be contacted again.

Potential Veterans identified through VADIR will initially be contacted by the STEP-Home study via a written outreach letter (sent via USPS mail or email). If the Veteran does not reply to STEP-Home's initial outreach, STEP-Home staff will make up to two attempts to contact the Veteran by phone, and the phone outreach attempts will begin at least 1 week after the written outreach letter was sent.

***Inclusion Criteria:*** Participants will be (1) Post-9/11 Veterans who report some reintegration, readjustment, or anger difficulty – i.e., Veterans who report “some difficulty” (Likert rating) on at least one of the primary measures: M2CQ; PDRI; STAXI-2; (2) 18-75 years old; (3) English-speaking (sessions will be conducted in English); and (4) Agreeing to participate (i.e., completion of ICF/HIPAA).

***Exclusion Criteria:*** Participants will be *excluded* for (1) schizophreniform disorder/active psychosis; (2) bipolar disorder; (3) active suicidality/homicidality requiring crisis intervention; (4) other severe psychiatric disorders prohibiting appropriate group participation; (5) neurological diagnosis prohibiting appropriate group participation (excluding TBI); (6) current substance dependence; (7) \*current participation in any other form of active behavioral therapy at the time of enrollment (e.g., Cognitive Processing Therapy, cognitive rehabilitation for mTBI, or other psychotherapy).

*\*For any potential participants who are currently participating actively in another treatment, they will be invited to participate in the next available cohort after their current treatment is complete.*

Enrolled STEP-Home participants will be instructed not to schedule initiation of another behavioral therapy until the 12-week intervention is complete. Importantly, Veterans will be allowed and encouraged to initiate any other treatment at the conclusion of STEP-Home or PCGT, even during the 12-week follow up. If another form of intervention is pursued during the actual 12-week intervention despite instruction to wait, we will allow participants to remain enrolled and track that information for use in statistical analyses similar to the 12-week post-intervention follow up period. We will, however, seek replacement participants for those who do this so that our statistical power is not diluted. Any necessary treatment for psychiatric crisis will also be allowed and tracked. Treatment enrollment and health utilization data will be collected at T1, T4, and T5 via self-report format and via CPRS chart review (please see Secondary Outcome Measures and Baseline Characteristics, protocol page 7). Psychotropic medication (and related visits) will be allowed if stable.

Note: If Veterans enrolled in STEP-Home express active suicidality/homicidality requiring crisis intervention, study staff will follow typical VA procedures including contacting Suicide Prevention Program and/or referring to Urgent Care. STEP-Home will not be seeing patients during off hours at the VA. The lead investigator ([name]) and lead therapist ([name]) are licensed psychologists. Appropriate safeguards will be in place if screening procedures, assessments, or intervention sessions cause any psychological distress or a psychiatric emergency emerges among participants. Staff will provide appropriate referrals and assess risk. If a psychiatric emergency is reported by a participant in the context of the study, the site PI, or in case of her unavailability, a Co-I ([name]) will contact the disclosing participant by phone, assess for risk and safety, and provide the participant with appropriate referrals. We will utilize access to local and national mental health resources available through the VA, including the suicide prevention hotline, risk assessments through Mental Health during regular business hours (Psychiatry Urgent Care), or the Psychiatrist on call during off hours. All potential collaborators on these research activities will have completed comprehensive training in the areas of research ethics, protection of human subjects, and suicide prevention. They will also have completed all VA required trainings pertinent to cyber security, VHA privacy policy (HIPAA), research data security and privacy, ethical principles of human subjects' protection, etc., as required by local IRBs.

*Informed Consent Process:* The informed consent process will take place prior to participation in the study either by mail, online via VA-approved technologies, or in quiet designated testing space with the Project Coordinator and/or other trained study staff members. If informed consent takes place online, the process is done individually for each participant with one study staff member; the consent process will never take place in a group format with more than one participant at a time. During the informed consent process, participants are informed that at any point in time, they are welcome to ask questions or bring up any issues that may concern them. They can tell the research assistants, project coordinator, and/or the investigator. If the investigator is not immediately available, the research assistants and project coordinator will relay the participant's question or concern to the investigator as soon as she is available. Participants are also given the investigator's phone number, and they are welcome to call her at any time during or after their study participation is completed.

If consent takes place via mail or online:

- Consent forms will be mailed via postal mail or sent via MyHealtheVet.

Consent forms will be reviewed with study staff and verbal consent will be obtained online on VA-approved technologies at the Pre-Visit (online questionnaire session), which is conducted in a private, individual session with one participant at a time. The participant will then be asked to sign the consent on camera via approved online platform and either: return signed document by mail (USPS); fax the signed document; taking a digital image and sending it via Azure RMS encrypted email; by study staff obtaining a screen capture of the signature page; or by electronic/digital signature. For the option of electronic/digital signature, this can be done by a signature made on a touch device or computer mouse, or through the use of DocuSign software.

*Payment:* Participants will be reimbursed \$20 for participation in assessments at Weeks 1, and 12. For the follow-up assessment at week 24, participants will be reimbursed \$40. There is no compensation for the skills-checks at weeks 4 and 8. Maximum total payment for assessments will therefore be \$80. Participants will also

be reimbursed up to \$120 for travel to/from the workshops over the 12 weeks. Participants will receive \$10/workshop for each workshop attended, regardless of distance/time traveled. Total maximum payment is therefore \$200. Payment may be in the form of a check, debit card, or electronic direct deposit.

October 2022 protocol update: If a participant signed a previous version of the consent form when direct deposit was not an option, we will contact them at the time of their next scheduled assessments and give them the option of re-signing the newer consent form so they can receive payment via direct deposit, if they so choose.

*Methods and Materials:*

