When a cohort large enough is available, randomization into STEP-Home or PCGT will occur and participation in the study begins (i.e., Time 1; T1: Pre), during which we will consent, administer the baseline assessments, randomly assign to either the STEP-Home or the PCGT arm, and schedule the treatment sessions. All participants will be assessed at the following 5 outcome points: Screening, at randomization (T1: Assessment), during treatment 4-week skills check (T2: Brief Skills Check), during treatment 8-week skills check (T3: Brief Skills Check), post-intervention (T4: Assessment), and at 3-months follow up (T5: Assessment). Assessments and skills checks are all self-report; therefore, blinded assessors are not required. Participants who decide to leave the program early will be asked to complete all assessments via secure Qualtrics link sent in MyHealtheVet or via postal mail service according to the RCT timeline following the intent-to-treat format, but will not be required to do so. Veterans will participate in their assigned treatment arm 1 day/week for approximately 2 hours. Replicating our SPiRE feasibility and preliminary effectiveness study [1], staff members will work in pairs when running groups. These same two staff members will offer to meet individually with Veterans before or after group approximately 4 to 6 times/workshop; it will be the Veterans' choice whether they participate in these individual meetings.

Assessments (T1, T4, and T5) may be done in person or online (see Data Security Section for description of Qualtrics online data entry). Brief Skills Checks (T2 & T3) may also be done in person or online.

**Randomization Figure.** T1 = Baseline Assessment; T2 = 4-week Skills check; T3 = 8-week Skills check; T4 = 12-week Post-Intervention Assessment; T5 = 24-week Follow-up Assessment.

- Assessments = T1, T4, and T5; Reimbursement = \$20
- Brief Skills Checks = T2 & T3; Reimbursement = \$0

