## **(3) Treatment Adherence and Program Satisfaction Measures**

### *Feasibility/Adherence*

- Supervisor Adherence: Supervisor Assessment of Therapist Adherence to Content
- Therapist Adherence: Therapist Self-Assessment of Adherence to Content
- Fidelity to Content: Participants rate fidelity to content
- Program Satisfaction: Participants rate interest, pace of delivery, and relevance of workshop goals with global and specific satisfaction ratings
- Participant Skills Self-Rating: Knowledge of core skills/key therapeutic ingredients
- Connectedness to VA services measure: Participants rate perceptions of engagement to treatment and VA

Therapist adherence to each intervention (STEP-Home and PCGT) will be rated by a supervisor. Therapists will be informed of these adherence ratings during training. Treatment adherence is an essential element of RCT design and these ratings will be required for all therapists.

Domain	Screening	T1 Baseline 0 weeks	T2 Skills check 4 weeks	T3 Skills check 8 weeks	T4 Post- Intervention 12 weeks	T5 Follow up 24 weeks
Baseline Characteristics						
Demographics	X					
Deployment data	X					
Active problems/diagnoses	X	X			X	X
Medication list	X	X			X	X
Health utilization data	X	X			X	X
WTAR	X					
Primary Outcomes						
M2CQ	X	X			X	X
PDRI	X	X			X	X
STAXI-2	X	X			X	X
Core Skills/Key Ingredients						
PSI		X	X	X	X	X
DERS		X	X	X	X	X
ARCES		X	X	X	X	X
Secondary Outcomes						
Mental Health						
PCL		X			X	X
DASS-21		X			X	X
NSI		X			X	X
Functional/Vocational						
WHODAS-2.0		X			X	X
SWLS		X			X	X
Treatment/Activities						
Survey						
BESI		X			X	X
Average hours worked		X			X	X
Cognitive Outcome						
FrSBe		X			X	X
Feasibility & Program Satisfaction						
	X	X	X	X	X	X

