Statistical Methods by Research Aims. The primary analysis for each aim will use an intent-to-treat (ITT) approach (i.e., all randomized subjects will be used in the analysis). ITT is optimal since it provides the least biased estimate of the treatment effect and the randomization balances STEP-Home and PCGT groups on known and unknown baseline confounders. This approach is appropriate for the proposed study given an anticipated low attrition rate of ~17% (based on attrition rates observed in our SPiRE study and Mt. Sinai's STEP RCT). We will implement quality assurance procedures to minimize protocol deviations and ensure correct treatment assignment according to the randomization. As a sensitivity analysis, we will conduct a per-protocol analysis in the subset of participants who complete an adequate amount of treatment ( $\geq 80\%$  of weekly sessions). We will assess the assumptions of homogeneity of variance and normality of residuals for each regression model and apply an appropriate transformation of the outcome if needed. We will address missing data, under the assumption of missing at random, using multiple imputation. Any subject characteristics associated with both the treatment group and primary outcome measure will be adjusted for in the final statistical model as specified in each aim.

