**Aim 1. Examine treatment effects of STEP-Home on primary outcomes relative to PCGT:**

***Hypothesis 1A. Participants randomized into the STEP-Home intervention will show improvement on reintegration, readjustment, and anger post-intervention (expressed by lower scores; less difficulty).***

Military to Civilian Questionnaire (M2CQ), Post-Deployment Readjustment Inventory (PDRI), and State-Trait Anger Expression Inventory (STAXI-2) scores post-intervention (T4)  $<$  baseline (T1)

Statistical Methods: Paired t-tests will evaluate the difference between pre- (T1) and post-scores (T4), with a separate analysis for each primary outcome.

***Hypothesis 1B. Participants randomized into STEP-Home will show greater improvement in primary outcomes as compared to PCGT.***

1B.1: Change scores baseline (T1) to post-intervention (T4) STEP-Home  $>$  PCGT

1B.2: Post-intervention (T4) primary outcome scores STEP-Home  $<$  PCGT

Statistical Methods: Mixed models (PROC MIXED in SAS) will evaluate pre-post differences, with a separate model for each primary outcome. The Satterwaite option will be used to account for the clustering of subjects within cohorts (identified in Section 6.2) and calculate degrees of freedom accounting for any missing data. Group (STEP-Home/PCGT) will be the between-subjects factor and time-point (T1/T4) will be the within-subjects factor. We hypothesize that there will be a significant interaction between group and time-point, with a larger improvement between pre- (T1) and post-scores (T4) in STEP-Home than PCGT. While we do not anticipate a significant interaction by cohort or site, we will evaluate the 4-way interaction and all 2-way and 3-way interactions for time-point, group, cohort, and site. The model will be rerun removing any non-significant interactions. Linear regression will be used to evaluate the difference in post-intervention (T4) by group. The final mixed and regression models for each outcome will adjust for any identified confounders.

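### The Hypothesis 1B.2 regression of T4 on arm names no baseline score, although M2CQ, PDRI and STAXI-2 are each measured twice before randomisation

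*Combined protocol and SAP*

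**What the plan says.** All places are in the combined protocol and SAP.

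- **Entry** (4(c) Human Studies, Inclusion Criteria): a Veteran qualifies by reporting some difficulty "on at least one of the primary measures: M2CQ; PDRI; STAXI-2".
- **Schedule** (table under Treatment Adherence and Program Satisfaction Measures): M2CQ, PDRI and STAXI-2 are each marked at Screening, at "T1 Baseline 0 weeks", at T4 and at T5. Section 4(b), Study Design, likewise lists "Screening, at randomization (T1: Assessment" as separate points.
- **Order** (4(b)): at T1 staff will "administer the baseline assessments, randomly assign to either the STEP-Home or the PCGT arm", so T1 is complete before allocation.
- **Hypothesis 1B.1** (Aim 1, Statistical Methods): a mixed model in which "time-point (T1/T4) will be the within-subjects factor". The test is the group-by-time interaction, and Aim 2 refers back to this model.
- **Hypothesis 1B.2** (same place): "Linear regression will be used to evaluate the difference in post-intervention (T4) by group". No baseline score is named.
- **Covariate rule** (Analytic Plan, Statistical Methods by Research Aims): "Any subject characteristics associated with both the treatment group and primary outcome measure will be adjusted for in the final statistical model".
- **Hypothesis 1A**: paired t-tests of T1 against T4.

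No inferential analysis names the screening score, and no analysis by baseline difficulty on a given outcome is prespecified.

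**The concern.** The baseline value of a self-report scale is usually among the best predictors of its later value. In a randomised comparison of T4 scores, a baseline covariate removes variance that has nothing to do with treatment, whether or not the arms happen to differ at baseline. The plan's rule makes adjustment depend on a chance association with arm. In most realisations the most useful covariate would stay out, and whether it enters would depend on the data. The trial would have two pre-randomisation readings of each primary outcome, yet its T4 regression would be assured of neither.

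What is at stake is precision and a fixed model, not bias. It matters somewhat more here because the Analytic Plan says that enrolment and completion of measures are slightly below the initial goals, and a one-year extension was obtained partly to protect power.

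**Working it through.** **1. Reproduce the plan's figure.** From Power Analysis: d = 0.44, one-sided 5%, 80% power, ICC 0.04, attrition 20%. From Study Design: target treatment group size 8.

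- Two-sample t-test (noncentral t): 65 per arm, power 80.2%.
- Design effect: 1 + (8 − 1) × 0.04 = 1.28.
- Total: 2 × 65 × 1.28 / 0.80 = 208, as stated.
- In reverse: 208 × 0.80 / 1.28 = 130, or 65 effective per arm.

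No baseline score enters this calculation, so the point exposes no error in it.

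**2. One baseline in the T4 regression.** Take equal SDs, d scaled to the T4 SD, and the design effect held at 1.28. The variance factor is 1 − r², where r is the correlation of the baseline with T4. Adding a second, equally correlated baseline changes it to 1 − 2r²/(1 + r). The effective d is 0.44 divided by the square root of the factor. The documents give no correlations, so r is assumed.

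| r | Factor, T1 only | Power | Factor, T1 + screening | Power | Further cut |
|---|---|---|---|---|---|
| none | 1.00 | 80.2% | – | – | – |
| 0.3 | 0.91 | 83% | 0.862 | 85% | 5% |
| 0.5 | 0.75 | 89% | 0.667 | 92% | 11% |
| 0.7 | 0.51 | 97% | 0.424 | 99% | 17% |
| 0.8 | 0.36 | 99% | 0.289 | above 99% | 20% |

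Most of the gain comes from naming T1 at all.

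**3. Correlation that decays with time.** Assume 0.8 (screening–T1), 0.6 (T1–T4) and 0.55 (screening–T4).

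- T1 only: 1 − 0.36 = 0.640.
- Both: 1 − (0.36 + 0.3025 − 2 × 0.6 × 0.55 × 0.8)/(1 − 0.64) = 1 − 0.1345/0.36 = 0.626.
- Further cut: 1 − 0.626/0.640, about 2%.

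**4. The 1B.1 interaction.** With complete data this is a difference in T4 − T1 change. Its variance per person is 2(1 − r) and its standard error is √(2(1 − r) × 2/65): 0.1754 at r = 0.5, 0.1109 at r = 0.8 and 0.1569 in the decaying case (T1–T4 correlation 0.6).

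- *Screening as a main effect, or as an extra time point with free arm means:* the standard errors are identical. A subject-level main effect cancels from T4 − T1.
- *Screening-by-time term:* the variance becomes 2(1 − r) minus the squared difference between the screening–T4 and screening–T1 correlations. With equal correlations nothing is gained. In the decaying case it is 0.80 − (0.55 − 0.80)² = 0.7375, a cut of about 8%.
- *Arm means constrained equal before randomisation:* the variance is that of the covariate-adjusted T4 comparison. At r = 0.5 the standard error is √(0.75 × 2/65) = 0.1519 with T1 only and √(0.667 × 2/65) = 0.1432 with both. In the decaying case they are √(0.640 × 2/65) = 0.1403 and √(0.626 × 2/65) = 0.1388.

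The constrained model is therefore the more dependable of the last two.

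**The case against.** **An unused option is not a defect.** The plan contains no contradiction or bias on this point, and 208 reproduces exactly. That stands, and it limits the weight of the point.

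**The gain depends on unknown correlations.** This also stands. The documents do not state the interval between Screening and T1 either. The increment from screening could be very small, and the case rests mainly on T1.

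**Averaging screening and T1 would do more.** A reader might calculate a 25% cut in change-score variance from replacing T1 by the mean of the two readings. That holds only if all correlations are equal. In the decaying example it is about 6%: 1 + (2 + 1.6)/4 − (0.6 + 0.55) = 0.75, against 0.80. Averaging could also carry regression to the mean into the uncontrolled 1A test if screening scores decide entry.

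**Stronger readings.** A reader might infer that screening scores serve only for entry. The documents do not say so: descriptive statistics are planned at each time point, pre-intervention values are compared between arms, and unnamed moderators may be added. A reader might also infer that the trial cannot identify Veterans who entered with no difficulty on an outcome. That is wrong, because both T1 and screening scores identify them; the plan only omits to prespecify such an analysis.

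Lastly, a reader might put a figure on power lost to a floor effect. The share with no room to improve appears nowhere. Some dilution may already sit inside d = 0.44, since the pilot subset was chosen by a similar any-of-three rule (M2CQ, WHODAS or IAS). Nor is lacking some difficulty on an instrument shown to mean that its score cannot fall.

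**Conclusion.** The point holds as one of modest efficiency and prespecification. The 1B.2 regression names no baseline score, the covariate rule would bring one in only on observed imbalance, and the screening score is in no specified model.

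The gain from one baseline is r² of the variance of the T4 comparison. For assumed r of 0.3, 0.5 and 0.7, power goes from 80% to 83%, 89% and 97% at 65 effective per arm. Screening on top of T1 gives a further 5% to 20% if all correlations are equal, and about 2% in the decaying case. These figures assume equal SDs and an unchanged design effect. They do not show that the trial is underpowered, and they leave 208 as it is.

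Any floor effect is of unknown size and does not carry this point.

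**What to change.** In the Statistical Methods for Aim 1:

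1. **1B.2.** For each primary outcome, prespecify the T1 score of that outcome, plus its screening score where available, as covariates in the between-arm regression at T4, regardless of observed imbalance. Exempt these scores from the general covariate rule.
2. **1B.1.** Fit the mixed model with arm means constrained equal at the pre-randomisation time points. A screening-by-time term is an alternative, but it helps only if screening correlates differently with T1 and with T4. A screening main effect or an unconstrained extra time point does not sharpen the T1/T4 contrast.
3. **1A.** Keep screening scores out of the pre-post test, because they may select for entry.
4. **Optional.** Since entry needs difficulty on only one of the three measures, prespecify one supportive baseline-severity-by-group analysis per outcome, to help in reading a null. An interaction with the continuous T1 score needs no cut-off. A subgroup would first need a definition of some difficulty on each scale. The analysis of all randomised participants stays primary.

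The cost is SAP wording, one or two degrees of freedom per model, and simple imputation of missing baseline scores. The scheduled assessments do not change. The optional item adds three supportive results.
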